The sample size was generated using G*Power (Version 3.1.9.6). Using the peak power variable in a study analysing ASH and muscle soreness (Diehl, 2021), the estimate of the effect size of Cohen's d equals to 0.53 and therefore used in the sample size calculation for this proposed research. There is no further calculation to convert Cohen's d into Cohen's f to make it appropriate for ANOVA, as when there are only two groups Cohen's f is the same as Cohen's d (University of Michigan, 2021). Using ANOVA repeated measures between factors, effect size of 0.53, 80% power, 5% risk error in a two-parallel-group design and three measurements, the overall sample size is 30 participants, with 15 subjects per group. The calculation provided by G*Power can be found in the appendix.

Selection criteria

Inclusion for participants who are:

- Female
- Playing football professionally
- At a sub-elite to elite standard

- Healthy and free of disease

Exclusion for participants with:

- Active supplementation with other ergogenic aids
- Medication or contraceptives (to not interfere with existing treatment)
- Thyroid conditions (due to interaction with cortisol)
- Diabetes or certain autoimmune conditions (to not interfere with existing treatment)
- Active pregnancy (to not interfere with existing treatment)
- Allergies to nightshades such as tomato, aubergine, potatoes and peppers (as ASH is an herb in the nightshade group)
- No signing of the consent form

The withdrawal criteria will be participants who request to withdraw and do not wish to proceed, or do not complete the required study tests.

Intervention

The intervention will be 600mg of KSM-66, a branded supplement derived from the root extract of the herb ashwagandha, with a consistent rate of 5% withanolides for 28 days. It is the most clinically studied extract of the herb and is the only type of ashwagandha to receive third party testing certification (Informed Sport, Informed Ingredient, BSCG, Clean Label Project). The laboratory where the product is made, Ixoreal Biomed, has received Current Good Laboratory Practices (cGLP), quality controlled and tested against heavy metals and pesticides.

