Food diary analysis research, compared against (Dobrowolski et al., 2020):

- Energy intake (kcal)
- Energy availability (kcal/kg fat free mass/day)
- Protein (g/day)
- Carbohydrates (g/day)
- Fat (%)
- Fluids (L/day)
- Vitamin D (mg/day)
- Calcium (mg/day)
- Iron (mg/day)

All data will be collected via Snap-N-Send and stored using Nutritics dietary analysis software (Research Edition, v5.096, Dublin, Nutritics, 2019). The Snap-N-Send method was analysed in a doubly labelled water study and was shown to have enhanced validity for assessing athlete total energy intake (Costello et al., 2019). The Nutritics software was clinically studied to be a useful and valid tool for healthcare professionals to measure macronutrients and micronutrients, demonstrating that its analysis values positively correlated with plasma markers (Watkins et al., 2020)

Independent:

- The treatment of ASH: 600mg KSM66 (30mg withanolides) once a day for 28 days

Data collection

Study data will be collected manually and entered into Blanquerna's OneDrive system. All data sheets and files will be backed up on to Google Sheets and shared with associated researchers and tutors of the project. This allows for data to be reviewed by collaborators.

Dietary intake data will be collected via Whatsapp using Snap-N-Send. The data will then be manually entered and stored using Nutritics and access will be shared with collaborators.

Data analysis

For the muscle strength and recovery research, dependent variables will be described as the mean and standard deviation and calculated using and **ANOVA repeated measures, between factors** as there will be three time points. A descriptive analysis will be carried out for all the data collected in the data collection notebook. To assess the normality of the data distribution, the **Kolmogorov-Smirnov** test will be used.

For the food diary analysis, dependent variables will be described as the mean and standard deviation and determined using **one-sided t-test** to compare against data averages of nutritional recommendations for female footballers (Dobrowolski et al., 2020). **Pearson's r** will be used to examine correlations between the selected variables.

Ethical considerations

The ethical considerations for this study are predominantly the safety, comfort and consent of the participant:

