There is high social relevance and value for the female athlete population, who are likely to experience strict training schedules with limited recovery time between training and matches. If significant benefits are found in recovery from ASH, there is a safe and low-cost method for athletes to adapt into their routine. Additionally, if there are benefits found in this thesis, practitioners who work directly with female athletes will be informed of up-to-date practice with ASH and can pass on information to athletes. Importantly, if the thesis shows no benefits across any measures, both athletes and practitioners will be informed of the supplement and its credibility.

The study holds high social and innovative relevance as it will collect, summarise and present existing published research that indicates a) overuse in high dosage and duration may lead to consistently lowered cortisol and b) consumption of solely root extraction of the herb is highly recommended in order to avoid potentially ingesting the cytotoxic metabolites of Withaferin A and Withanone, which are found in the leaves of the herb. Providing safety and information for users and future users of ASH is the crux of this thesis.

Scientific-technical validity

All of the instruments and questionnaires used in the proposed study are established in peer-reviewed literature and deemed both valid and reliable. Two measures will be taken for each tool. The first instance will be the baseline measure and will occur on-site at the training ground gym in the evening during a typical training session. The second measure will take place after 28 days of supplementation (half ASH, half placebo) in the same location and time of day. Each participant will be given a timeslot to enter the gym and perform their assessments before continuing with normal resistance-training session. The tests using instruments will be monitored by two strength and conditioning coaches, and the data will be collected by two sports scientists. The following evaluation instruments are as follows:

- Hand grip strength of the participants will be measured with a CAMRY dynamometer and the predominant measure to assess muscle strength. It is a commonly used tool in sports performance and demonstrates validity and reliability in relation to athlete

strength (Cronin et al., 2017). The validity for the use of a CAMRY dynamometer is documented by (Huang et al., 2022) when comparing against the Jamar dynamometer.

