There is no known conflict of interest in this study. There will be no plagiarism within this study and all words will be original to the study. There will be no fabrication or invention of results, and data will be analysed and published accurately and transparently. All collaborators will be employed staff members of the football club who are collaborating in the thesis. The gym facilities where the tests will be measured and performed are on-site of the football club and where the players have weekly gym training sessions. The gym facility is a licensed establishment. The participants will be informed of the results and will have access to their individual data.

Work plan

A visual representation of the study timeline can be found in the appendix. A description of each step is as follows:

0. Approval from the ethical committee
1. Participants are informed about the aims of the study and sign the consent form. Information about age, BMI, years of practice and health history is collected
2. Participants start tracking their food diaries via an app remotely for three days over the weekend prior to the supplementation for familiarisation
3. Baseline measures for muscle strength will be taken on the following day at the club gym, coinciding with a regular gym training session. The measures will be taken prior to starting a typical training session
4. The team will consist of the author ([name]), [name] and [name] who will assist with data collection and physiotherapist [name] who will monitor participants and their safety while performing the strength tests

5. Afterwards participants will be given a printout of the TQR questionnaire and the Hooper Index to complete for the next day. Participants will be given their course of supplementation, either placebo or KSM-66, and instructed to take one a day for 28 days
6. The following day, baseline measures for the muscle recovery will be collected remotely at midday via Whatsapp or Zoom, and at the same time participants will start supplementation of either KSM-66 or placebo
7. Fourteen days later, participants perform the muscle strength tests in the evening at the club gym. Similar to before, the team will consist of the author ([name]), [name], who will assist with data collection and physiotherapist [name] who will monitor participants' safety while performing the strength tests

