8. Afterwards participants continue with the regular gym training session. Printouts of TQR and Hooper Index questionnaires are given to participants for the next day
9. The following day muscle recovery measures are collected remotely via Whatsapp or Zoom at midday
10. An additional fourteen days later, participants finish supplementation and perform the muscle strength tests in the gym with identical circumstances (staff, equipment, temperature) as the previous two gym sessions
11. The following day muscle recovery measures are collected remotely via Whatsapp or Zoom at midday. The trial finishes
12. The analysis of data begins
13. The process dissemination of results and findings begins

The study is designed with ease of participation in mind, but there will be inconveniences for participants who forget to take the intervention or fill out the food diary. To alleviate this, participants will be notified (with permission via the consent form) over Whatsapp with reminders during the 28 days supplementation. Additionally, there will be a check-in session a week after supplementation starts, to assess participant satisfaction and compliance.

Resources

Primary resources will consist of raw data through observation obtained from gym equipment and hand grip dynamometer and first-hand accounts from participants when answering

subjective questionnaires and food diaries. Secondary resources will consist of Excel and Google sheets to store the data, SPSS software to analyse the data, and Nutritics software to analyse the dietary intake.

The facility where the baseline and post-supplementation muscle strength tests are performed will take place at the club gym for CE Seagull (located at [name]). Participants will be familiar with the facility and its equipment due to previous weekly gym training sessions prior to any measurements.

Applicability and limitations

Applicability

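### One section gives two measurement occasions where the rest of the plan gives three, and the named ANOVA, read as a group main effect, does not isolate the day-28 difference under either schedule

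*Combined protocol and SAP*

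**What the plan says.** The section on scientific-technical validity, which introduces the instruments, states "Two measures will be taken for each tool". It defines the first as the baseline measure and continues "The second measure will take place after 28 days of supplementation". No day-14 measure is mentioned there.

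Three other sections describe three occasions:

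- Sample size: the calculation is for a "two-parallel-group design and three measurements", using repeated-measures ANOVA, between factors, with an effect size of 0.53, 80% power and a total of 30 participants.
- Data analysis: the same ANOVA is chosen "as there will be three time points".
- Work plan: step 3 is "Baseline measures for muscle strength will be taken on the following day at the club gym"; step 7 is "Fourteen days later, participants perform the muscle strength tests in the evening at the club gym"; step 10 is "An additional fourteen days later, participants finish supplementation and perform the muscle strength tests in the gym with identical circumstances". TQR and Hooper Index scores are collected on the day after each session.

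The section on scientific and social value frames the question as whether the supplement gives performance benefits after 28 days. The data analysis section names no contrast at day 28 and does not say which ANOVA term will be tested.

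**The concern.** The number of occasions is a basic design parameter, and the plan gives two values for it. Staff working from the instruments section alone would leave out the day-14 session. That session cannot be recovered later, and the three-time-point analysis depends on it.

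The count also matters because of the test that is named. A group main effect in a repeated-measures ANOVA compares each group's mean over all its occasions. One of those is baseline, taken before supplementation, where randomisation makes the expected group difference zero. The tested quantity is therefore a diluted version of the day-28 difference. The dilution depends on how many occasions are averaged and on how early the effect appears. At stake are the meaning of the reported estimate and the power of the trial to detect an effect at the time the protocol asks about.

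**Working it through.** **1. Occasions by section**

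| Section | Baseline | Day 14 | Day 28 |
|---|---|---|---|
| Scientific-technical validity | yes | no | yes |
| Sample size | three measurements, days not named | | |
| Data analysis | three time points, days not named | | |
| Work plan, steps 3, 7, 10 | yes | yes | yes |

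The sentences that follow the two-measures statement fix its meaning as visits, so it cannot mean two attempts per visit.

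**2. The plan's own sample size**

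Inputs from the sample size section: f = 0.53, alpha 0.05, power 80%, two groups, m = 3. The correlation ρ among occasions is not in the available text (the G*Power output in the appendix is not shown), so it is assumed over 0.5 to 0.9.

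Formula: λ = N f² m / (1 + (m − 1)ρ), with 1 and N − 2 degrees of freedom, taking the smallest even N with power of at least 80%.

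Example at N = 30, m = 3, ρ = 0.9: λ = 30 × 0.2809 × 3 / 2.8 = 9.03, power 82.6%.

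| ρ | N, three occasions | N, two occasions | Power at N = 30, three / two |
|---|---|---|---|
| 0.5 | 22 | 24 | 92.9% / 89.9% |
| 0.7 | 26 | 26 | 87.9% / 86.0% |
| 0.8 | 28 | 28 | 85.3% / 84.0% |
| 0.9 | 30 | 30 | 82.6% / 82.0% |

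The stated 30 is met exactly with three occasions if ρ is about 0.9. Whether that was the value used cannot be determined.

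**3. What the group main effect estimates**

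Let D be the day-28 difference, with an expected baseline difference of 0.

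- Two occasions: (0 + D)/2 = 0.50D.
- Three, full effect by day 14: (0 + D + D)/3 = 0.67D.
- Three, linear build-up: (0 + 0.5D + D)/3 = 0.50D.
- Three, no effect at day 14: (0 + 0 + D)/3 = 0.33D.

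**4. Power with 15 per group**

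For two equal groups f is half the standardised difference, so f = 0.53 means 2 × 0.53 = 1.06 SD. Take D = 1.06 SD, a two-sided 5% test, equal variances and one common ρ.

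- Averaged test: the SD of a participant's mean is √((1 + (m − 1)ρ)/m), the non-centrality is effect / (SD × √(2/15)), with 28 df. Example, three occasions, full effect by day 14, ρ = 0.5: 0.707 / (0.816 × 0.365) = 2.37, power 62.9%.
- Day 28 adjusted for baseline: the residual SD is √(1 − ρ²), with 27 df. At ρ = 0.5: 1.06 / (0.866 × 0.365) = 3.35, power 89.8%. At ρ = 0.8: 1.06 / (0.600 × 0.365) = 4.84, power 99.7%.

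| Test | ρ = 0.5 | ρ = 0.8 |
|---|---|---|
| Averaged, two occasions | 36.7% | 31.5% |
| Averaged, three, full by day 14 | 62.9% | 51.9% |
| Averaged, three, linear | 40.4% | 32.5% |
| Averaged, three, none at day 14 | 20.8% | 17.1% |
| Day 28 adjusted for baseline | 89.8% | 99.7% |

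These averaged-test figures fall below those in step 2 because the formula there takes 1.06 SD as the difference in the averaged means, as if it were also present before supplementation.

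**5. Sensitivity**

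If D is 0.53 SD, the value the protocol gives as Cohen's d, the adjusted day-28 comparison has 36.6% (ρ = 0.5) to 64.5% (ρ = 0.8) power. The averaged test has 7.9% to 20.8%. The ordering is the same, but neither reaches 80%.

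**The case against.** Three sections agree on three occasions, and the step-by-step work plan is the one staff would follow. Step 10 also refers back to two earlier sessions. A reader might infer that the day-14 visit will be missed and the planned ANOVA become impossible. The documents make that unlikely, so the contradiction is mainly a drafting error. This stands.

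A reader might also infer that the visit count undermines the sample size of 30. It does not. At the plan's f, the required N differs by at most 2 for correlations of 0.5 to 0.9: 24 against 22 at 0.5, and no difference at 0.7, 0.8 or 0.9. Power at N = 30 stays above 80% by the plan's formula with either count.

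Nor does the estimated effect always change with the count. With linear build-up it is 0.50D under both schedules, and with a late effect three occasions give less than two (0.33D against 0.50D).

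Finally, the data analysis section does not say which ANOVA term decides the result, and software would usually print a group-by-time interaction as well. Treating the group main effect as the test is an inference from the between-factors label and from the sample size calculation. It is the natural reading, but it is a reading. The dilution is also separate from the contradiction, since it remains once the count is corrected to three.

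**Conclusion.** The contradiction is real, and the validity section is the outlier. Taken alone it is a minor consistency error with little bearing on the sample size.

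The larger consequence is that no comparison at day 28 is named. If the between-factors ANOVA means the group main effect, it estimates between one third and two thirds of the day-28 difference with three occasions, and half with two. It therefore does not directly answer the stated question under either schedule. At 15 per group and D = 1.06 SD its power is 17% to 63%, against about 90% to over 99% for the baseline-adjusted day-28 difference.

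These figures rest on an assumed correlation of 0.5 to 0.8, equal variances, one common correlation and no dropout. They also take the plan's f at face value. At D = 0.53 SD the adjusted comparison is still the stronger test but falls short of 80%, so naming it does not by itself show that 30 participants are enough.

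**What to change.** 1. In the section on scientific-technical validity, replace the two-measures statement with a schedule per instrument. Strength tests and RPE take place at baseline, day 14 and day 28, with TQR and the Hooper Index on the day after each. A blanket change to three measures for every tool would be wrong. The supplement satisfaction questionnaire cannot be answered at baseline and is not among the work plan steps. The food diary is described in the work plan for three days before supplementation, and elsewhere as running through the study. Both need their own stated timing.
2. In the data analysis section, name the group difference at day 28 adjusted for baseline as the confirmatory comparison, with day 14 as supportive. The confirmatory estimate then does not depend on how many visits are averaged.
3. In the sample size section, restate the power for that comparison. Give the assumed day-28 difference in SD units and the assumed correlation between baseline and day 28.

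The cost is text changes in three sections and one new calculation, with no added visits, data or participants. Because the confirmatory analysis changes, the amendment should be dated and made before anyone sees results by group.

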- Improved perception of recovery
- Reduced difficulty of exertion during exercise

(Bonilla et al., 2021)

Potential side effects

Side effects of ASH are uncommon, however large doses (exceeding 1,250mg daily, based on a clinical trial examining tolerability) may induce:

- Direct irritation to the intestinal mucosa, resulting in:
 - Nausea
 - Vomiting
 - Gastrointestinal upset

(Raut et al., 2012, LiverTox, 2019)

Regarding the potential side effects of KSM-66 specifically, a trial by (Chandrasekhar et al., 2012) noted adverse effects in subjects after 60 days of 600mg KSM-66 supplementation. Overall, there were 6 adverse events with ASH and 5 with placebo. They included congestion, decreased appetite, cough and cold symptoms. The placebo group experienced fever, headache, tiredness and abdominal pain, making it unclear as to whether KSM-66 has notable or established side effects.

Intervention group

The intervention for the experimental group will be KSM-66 ashwagandha (600mg ashwagandha containing 30mg withanolides, once a day with meals for 28 days, ingested at midday) supplied by the company Zenement based in Barcelona. The branded product of KSM-66 is made by Ixoreal Biomed.

Control group

The control group will receive rice flour in a HPMC capsule, once a day with meals for 28 days, ingested at midday. The rice flour will be a commercial product found in supermarkets. To achieve randomisation, simple random allocation will be used to prevent bias amongst participants. The protocol will follow the randomisation guide by (Arifin, 2012) and will be

achieved in SPSS software. It will be a double-blind study as the main researcher will not know which participants supplement ASH or placebo.

Variables

Dependent:

Muscle strength research:

- Hand grip strength in kilograms (kg) using a CAMRY dynamometer. The variable of interest will be the mean of the right and the left-hand measurements
- Seated medicine ball throw in metres (m)
- Counter movement jump (CMJ) in watts per kilogram ($W \cdot kg^{-1}$)
- Squat jump (SJ) in centimetres (cm),
- Peak power in watts per kilogram ($W \cdot kg^{-1}$), using the results from SJ
- Rate of Perceived Exertion (RPE) via Borg Scale

Muscle recovery research:

- Perceived ratings of sleep, stress, fatigue and Delayed Onset Muscle Soreness (DOMS) via Hooper Index (HI)
- Total Quality Recovery (TQR) questionnaire
- Supplement satisfaction questionnaire

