There is minimal risk posed to participants involved in this study, as there are no reported harms from supplementing KSM-66 in clinical research and no adverse effects have been reported. Additionally, it is a commercially available product that has been certified safe to supplement. As KSM-66 is made from root extraction of the ashwagandha herb, and therefore not made of the leaves, there is less toxicological risk as the metabolites Withaferin A and Withanone are removed in the process (further elaboration in the *Thesis – Intervention* section of this document) making KSM-66 safer than other products of ashwagandha. Potentially, a participant could have an undiagnosed illness or allergy to nightshades and the supplement gives side-effects. Previous literature has not reported any instances of this happening. It is unlikely as athletes typically have a medical team at their disposal, who provide health checks and make sure they are fit to play. Due to the short-term time length and reasonable dosage of the study, there is minimal risk for over-supplementation leading to consistently reduced cortisol or gastrointestinal problems. There is low to no risk pertaining to psychological, social or economic factors. The study has been designed with participant comfort in mind and the timeline, training sessions, performance and recovery tests mimic the participants' usual regime, allowing for ease of participation and reduced risk factor.

The anticipated benefits outweigh the risks. The supplement of KSM-66 has shown to improve muscle strength, recovery, cognition and sleep in published literature. These are highly important factors to the lifestyle of an athlete and provide social, psychological and physical benefits.

Privacy

All personal data and information collected or generated in the study will be stored on OneDrive Blanquerna and protected in accordance with the current legislation on personal data protection (Regulation (EU) 2016/679 and in the Organic Law 3/2018 of 5 December on Data Protection). No one, except some of the staff directly related to this study, will be able to know the identity. Data will be stored only for the duration of the study and during the process of analysing the data.

Integrity

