There is a high likelihood that the study may impact the target population of female footballers and to athletes as a wider population. The supplement of KSM-66 is easily accessible, cost-effective and has Informed Sport certification, making it safe to ingest without the risk of contaminated ingredients. The supplement is already highly used in the area of sports performance; importantly, this study aims to verify whether short-term supplementation has benefits and will inform the wider population on safe dosage guidelines. This benefits not only athletes, but practitioners on best procedure for their patients or clients. Weekly gym sessions are an integral part of footballer's training regime, and if benefits are found in muscle strength, RPE and wellness scores of sleep quality, muscle soreness, stress and fatigue, athletes may wish to explore supplementation with KSM-66 to improve their strength output, perception of difficulty, sleep quality and muscle soreness with a safe method. Additionally, if athletes or active individuals experience high levels of stress and it affects their performance and recovery as a result, the study is applicable as the intervention may potentially improve these areas.

Limitations

Regarding participants, accuracy of food reporting and following supplementation guidelines will be based on trust between the author and participant. The study has convenience sampling, which allows for ease of data collection but lacks generalisability in the sample. The focus of the study is on subjective results, without the validity of physiological tests that could measure metabolic markers, such as cortisol, from blood samples. There is also a lack of

previous research on ASH and exercise in females and athletes, which impacts result credibility.

Dissemination plan

Full transparency of the measurements will be published within each of the corresponding three papers. No measurements or scores will be omitted. The purpose of the outreach is to contribute to the scientific knowledge of ASH and its effects on muscle strength and recovery in female athletes. Additionally, this research will provide scientific knowledge to sports science and the industry of sports nutrition of the influence of short-term ASH, and whether it provides any benefits to female athletes. The methods of sharing the scientific knowledge will include presentations at conferences, exhibitions, social media and published articles in journals.

References

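### The plan promises guidance on safe dosing but states no adverse-event recording and no harm-based rule for stopping capsules, and its benefit/risk premise conflicts with its own side-effects section

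*Combined protocol and SAP*

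**What the plan says.** **Promise.** Applicability says the study "will inform the wider population on safe dosage guidelines". Scientific and social value adds, more cautiously, that the research might yield new dosing guidance for users.

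**What is measured.** The Variables section lists strength and jump tests, perceived exertion, the Hooper Index, the Total Quality Recovery (TQR) questionnaire, supplement satisfaction and diet. Data analysis covers these and names no safety analysis.

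**Contacts.** The Work plan says "there will be a check-in session a week after supplementation starts, to assess participant satisfaction and compliance". Strength tests follow at about two and four weeks, each with recovery ratings collected remotely the next day. The physiotherapist "will monitor participants and their safety while performing the strength tests". Ethical considerations adds that the researcher may use contact details to check in with players, and the Work plan adds WhatsApp reminders.

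**Leaving the study.** Selection criteria: "The withdrawal criteria will be participants who request to withdraw and do not wish to proceed, or do not complete the required study tests". Ethical considerations says players are told of possible side effects and may leave at any time.

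**Safety premise.** Benefit / risk ratio bases its judgement of minimal risk on there being "no reported harms from supplementing KSM-66 in clinical research and no adverse effects have been reported". Potential side effects says that a trial "noted adverse effects in subjects after 60 days of 600mg KSM-66 supplementation", and continues: "Overall, there were 6 adverse events with ASH and 5 with placebo". It concludes that it is unclear whether the product has established side effects.

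**The concern.** A trial that means to advise on safe dosing needs some record of harm by arm. Here a player with nausea or stomach upset would meet no stated question about it. Her capsules would stop only if she asked to leave, or if she was withdrawn for not completing tests, and in neither case does the plan require a reason to be recorded. With no event record, ashwagandha and placebo could not be compared descriptively on tolerability. The ethical justification also rests on a premise that another section of the same plan contradicts.

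**Working it through.** The plan gives no figure of its own on this point. The check is a count of contacts, a comparison of sections and one bound.

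**1. Scheduled contacts after the first dose** (Work plan; days approximate)

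| Contact | Stated content | Adverse-event question stated? |
|---|---|---|
| Day 7 check-in | Satisfaction, compliance | No |
| Day 14, gym | Strength tests | No |
| Next day, remote | TQR, Hooper Index | No |
| Day 28, gym | Strength tests | No |
| Next day, remote | TQR, Hooper Index | No |

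The result is 0 of 5. Adding the remote contact that coincides with the first capsule makes 6 contacts, and adding the baseline gym visit makes 7. The number with a stated adverse-event question stays 0. The extra check-ins and the reminders have no fixed number, and none has a stated adverse-event question.

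**2. Could the existing instruments stand in?**

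- The Hooper Index rates sleep, stress, fatigue and soreness.
- The TQR form in the Appendix gives 8 of its 20 points to nutrition, 2 to hydration, 4 to sleep and rest, 3 to relaxation and emotional state, and 3 to stretching and cool-down.
- The satisfaction questionnaire has two ratings from 1 to 5.

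Poor appetite or an upset stomach could lower the meal items, and tiredness could raise Hooper fatigue. None of these instruments records an event, its date, its severity or what was done. None asks about nausea, vomiting or gastrointestinal upset (Potential side effects), or about emotional numbness, which the Justification of the study gives as a worry with long use.

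**3. Stop rule.** The withdrawal criteria are the player's own request and incomplete tests. Neither is a harm criterion. The physiotherapist's stated safety role is limited to the strength tests.

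**4. The two safety statements.** Benefit / risk ratio denies any reported adverse effects of KSM-66. Potential side effects reports 6 adverse events on ashwagandha and 5 on placebo with 600 mg KSM-66 over 60 days. The conflict is about whether events were reported, not about what caused them.

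**5. What 15 players on ashwagandha could show with full recording.** The 15 per arm comes from Sample size. If no player has an event, the one-sided 95% upper bound p for the proportion with an event solves (1 − p)^15 = 0.05:

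p = 1 − 0.05^(1/15) = 1 − 0.819 = 0.181, or 18.1%.

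The two-sided 95% interval has upper limit 1 − 0.025^(1/15) = 0.218, or 21.8%.

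The chance of seeing at least one affected player among 15 is 1 − (1 − p)^15. The true rates p below are assumed, because the documents give none:

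| Assumed rate | Chance of at least one |
|---|---|
| 1% | 14.0% |
| 5% | 53.7% |
| 10% | 79.4% |

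Recording makes events visible, but an arm of this size cannot show that the dose is safe.

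**The case against.** The best defence is that this is an efficacy study. Hypothesis and Objectives contain no safety aim, and the overclaim is essentially one clause under Applicability. Players are warned of side effects and may leave, and a club medical team is assumed to be available. The consent pages, the timeline figure and the contents of the data collection notebook cannot be read here, so a contact route or an event page may exist. All of this limits the point to the readable plan and keeps it minor. It does not supply a stated outcome or a stop rule, and a contact route in a consent form would be neither.

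Four stronger readings are tempting, and the documents do not support them.

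- **Safety as the trial's central deliverable.** Scientific and social value ends a paragraph with "Providing safety and information for users and future users of ASH is the crux of this thesis". That paragraph is about summarising published research, so the sentence does not promise trial safety data.
- **No problem could surface at all.** The check-ins, the reminders and the recovery scores could reveal some problems indirectly.
- **A forecast of events in this trial from the 6 and 5.** The arm size of that trial is not in the documents, so any forecast would depend on a guess. The near-equal split does not show harm from the product either.
- **Biased efficacy results.** Background illness would be expected in both randomised arms, and no shift in any outcome has been shown.

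**Conclusion.** The point holds for the readable plan, at minor severity. The plan ties dosing guidance to this study but states no adverse-event variable, no safety analysis, no adverse-event question at any of the five scheduled contacts after the first dose or at the other check-ins and reminders, and no harm-based rule for stopping capsules. The denial of reported adverse effects under Benefit / risk ratio is contradicted by Potential side effects and should be corrected whatever else is done.

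The count follows the three time points in the Work plan and Data analysis. The 18% bound assumes all 15 players on ashwagandha are followed and none has an event. Adding event recording therefore improves participant protection and reporting, but it would not turn the trial into evidence of a safe dose. Only narrower wording resolves that claim.

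**What to change.** 1. **Recording.** Add a short adverse-event form, completed under the blind in both arms at the existing contacts. It should have one open question plus a checklist of nausea, vomiting, gastrointestinal upset and emotional numbness. Report counts by arm descriptively, without a test.
2. **Selection criteria.** Add a rule to stop capsules for a suspected reaction, refer the player to the club medical team, record the reason, and continue her assessments where possible.
3. **Benefit / risk ratio.** Replace the denial of reported adverse effects with the 6 and 5 events given under Potential side effects, and say that the cause is unclear.
4. **Applicability.** Limit the claim to the efficacy of 600 mg daily for 28 days against placebo, and attribute any safety advice to the planned literature summary.

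**Cost.** No new visit, test or participant is needed. At an assumed 2 minutes per form, 5 contacts × 30 players × 2 minutes = 300 minutes, or about 5 hours, plus time to follow up reported events. A checklist will also draw out some minor complaints, in both arms.
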